10.2 Method of Assigning Subjects to Treatment Groups

At each investigated cohort, subjects will be randomized in the ratio of 6 active treatments to 2 placebos (3:1). For safety reasons, the subjects of each cohort will be divided in 2 sub-cohorts with 2 sentinel subjects in the first sub-cohort and 6 additional subjects in the second sub-cohort (see Section 8.1). The randomization schedule will be designed so that in each sub-cohort there will be 1 subject scheduled to receive placebo.

The randomization list will be performed by someone not directly enrolled in the research team. SAS software version 9.4 or higher will be used. The disclosure of the randomization schedule will be done at the end of the study or in case it is needed to provide convenient medical care to any subject due to AEs.

Following confirmation of eligibility, subjects will be assigned a subject randomization number at Baseline using an Interactive Response Technology (IRT) system in the order in which they are randomized in the study.

Only subjects receiving an IMP administration will receive a randomization number. Subjects who replace a discontinued subject will receive the same administration as the discontinued subject. This subject will receive a number that refers to the number of the subject that is being replaced.

In order to maintain the double-blind study, the administration of the IMP must occur individually and separately, and in the absence of the physician responsible for the study. This is because the reaction after its administration could be easily distinguishable between placebo and IMP.

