13. STATISTICAL METHODS AND DETERMINATION OF SAMPLE SIZE

13.1 Statistical and Analytical Plans

A separate statistical analysis plan (SAP), which will provide more details of the statistical analysis outlined below, will be prepared and approved prior to unblinding the study data. No formal statistical hypothesis of the safety or tolerability are to be tested for this study.

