13.1.5.1 Pharmacokinetic Analysis

ATL-001 plasma concentration data will be listed by treatment, subject and visit/sampling time point. Descriptive summary statistics will be provided by treatment, and visit/sampling time point, including the frequency (n, %) of concentrations below the limit of quantification and reported as zero.

Summary statistics will include mean (arithmetic and geometric), standard deviation, coefficient of variation (arithmetic and geometric), median, minimum, and maximum. An exception to this is t_{max} where median, minimum and maximum will be presented. Concentrations below limit of quantification will be treated as zero in summary statistics and for PK parameter calculations. A geometric mean will not be reported if the data set includes zero values. The PK data of all subjects who received at least one dose of ATL-001 and who have at least one valid PK measurement will be used in the PK set analysis.

A non-compartmental analysis will be used to calculate the PK parameters detailed on Section 11.2. A normalization by dose will be performed in the main PK parameters ($AUC_{(0-t)}$ and C_{max}).

Unassessable subjects for the PK analysis are:

Version: 4.0

Date: 13 December 2023

Sponsor: Atlas Molecular Pharma S.L. Study Code: ATL001-PI-CEP

NCT No.: 05647343

• Subjects who experienced an AE (e.g., vomiting) and took (or not) concomitant medication, if the experienced AE itself and/or the concomitant medication taken, interferes in a relevant manner with his PK results

- Subjects missing more than four samples throughout the study period.
- Excessive deviation between consecutive blood samples collection from scheduled time of sample collection (more than 10% of the time period between consecutive samplings)
- Subjects with lack of any measurable concentration or only very low plasma concentration for drug product*
- Subjects with non-zero baseline concentration > 5% of C_{max}*
- Subjects with less than three quantifiable concentrations*

*Except for these criteria, decision to exclude a subject from the statistical or PK analysis must be made before bioanalysis and has to be properly documented.

More details on the PK parameters, analysis and presentation of study results will be provided in the PK analyses SAP.

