13.2 Determination of Sample Size

The study will consist of five sequentially recruited cohorts of 8 subjects each, resulting in up to 40 randomized subjects.

No technical sample size calculation was done.

This sample size of 8 subjects per cohort with a randomization 3:1 for active/placebo treatment, is regarded sufficient to demonstrate the effects of the study drug under investigation and therefore to be sufficient to fulfill the objectives of the study.

In case of a withdrawn subject from the study during the treatment period and for other reasons than safety, he/she may be replaced with another subject, at the Sponsor's discretion. All subjects receiving at least one dose of the study medication will be evaluated for safety.

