3.2 PK Analysis Set

PK analysis set are defined as all randomized subjects who received at least one dose of the study drug medication and have sufficient data to estimate at least one PK parameter. Subjects with major protocol deviations that might have impacted the PK data collection will be excluded from the population.

PK analyses will be based on PK analysis Set.

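### The PK exclusion list in Protocol 13.1.5.1 selects partly on measured exposure and discards complete Day 1 profiles, and the SAP does not say whether the list still applies

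*Protocol*

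**What the plan says.** Protocol 13.1.5.1 lists six kinds of subject as unassessable for PK. Three matter here:

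- "Subjects with lack of any measurable concentration or only very low plasma concentration for drug product" (starred)
- "Subjects with less than three quantifiable concentrations" (starred)
- "Subjects missing more than four samples throughout the study period" (not starred)

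The footnote to the stars reads: "Except for these criteria, decision to exclude a subject from the statistical or PK analysis must be made before bioanalysis". The starred criteria may therefore be applied once concentrations are known. The third starred criterion, on pre-dose concentration, is not part of this point.

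The same section, shortly before the list, says that data from every subject with at least one ATL-001 dose and one valid PK measurement will be used. This matches the PK set in Protocol 13.1.1.

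SAP 2.4 records a changed PK set. Under SAP 3.2 a subject must "have sufficient data to estimate at least one PK parameter" and must have no major deviation that might have affected PK data collection. Neither of these sections nor SAP 5.4.4 mentions the protocol's list.

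**The concern.** The active compound is said to have precipitated in the stomach (Protocol 6.3), and ATL-001 is a new oral formulation tested for the first time in humans. Poor absorption in some subjects is therefore a result that the PK objective should show. A rule that removes subjects because their measured exposure is low selects on the outcome. With no threshold for very low, the choice is made with concentrations in hand: Protocol 11.2 releases them to the PK analyst after each cohort.

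The missing-sample rule has a different fault. It counts both profile days together, so a subject with a full Day 1 profile and no Day 5 profile is lost entirely. Gastrointestinal toxicity is the identified risk (Protocol 6.5), so early stopping need not be unrelated to dose or exposure.

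Each dose has at most six active subjects, so one exclusion is visible in the summary. Exclusions that fall unevenly across doses would also distort the comparison of dose-normalised AUC and Cmax planned in 13.1.5.1.

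**Working it through.** **1. Sample count.** Protocol 8.2.1.2 gives one pre-dose and 11 post-dose samples up to 12 h: 1 + 11 = 12 points, and 12 × 5 mL = 60 mL. This reproduces the figure in Protocol 11.2.1. Adding the 24 h sample gives 13 per profile, and 2 × 13 = 26 per subject, as in SAP 4.6. The limit of four is 4/26 = 15% of samples. A subject with no Day 5 profile misses 13, which exceeds four.

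**2. What each text does with the same subject.**

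| Subject | Protocol 13.1.5.1 list | Protocol 13.1.1 and inclusion sentence in 13.1.5.1 | SAP 3.2 |
|---|---|---|---|
| Full Day 1 profile, stops before Day 5 | Out | In | In (Day 1 parameters estimable) |
| One or two quantifiable values | Out | In | In (Cmax and tmax read directly, SAP 4.6) |
| Several quantifiable values, all low | Out or in, no threshold | In | In |
| No measurable value | Out | Depends on whether a below-limit result is valid; not defined | Probably out: no parameter to estimate |

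In each row at least two texts can disagree.

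**3. Size if a low exposer is removed.** The documents give no between-subject CV, LLOQ or expected number of exclusions. Assume log-normal exposure with CV 30%, 50% or 70%, so σ = √ln(1 + CV²) = 0.294, 0.472, 0.631. The expected lowest of six standard normal values is −1.267. The six sum to zero in expectation, so the other five average 1.267/5 = 0.2534. The geometric mean is then multiplied by exp(0.2534σ):

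- CV 30%: exp(0.0744) = 1.08
- CV 50%: exp(0.1197) = 1.13
- CV 70%: exp(0.1600) = 1.17

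Simulating 1,000,000 cohorts of six gives 1.077, 1.127 and 1.174, with the log-scale SD falling to 0.82 of its full-sample value. Removing the lowest two gives 1.15, 1.25 and 1.35, with the SD ratio at 0.70.

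This removes the lowest-ranked subject whatever the level. That subject sits on average at exp(−1.267σ) = 69%, 55% and 45% of the true geometric mean, which need not count as very low. For one subject at a fraction f of the geometric mean of the other five, exclusion multiplies the geometric mean by f^(−1/6): 1.12 at f = 0.5 and 1.47 at f = 0.1.

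**4. Chance that a rule bites.** At an assumed per-subject rate p, the chance of at least one of six is 1 − (1 − p)^6: 26%, 47% and 74% at p = 5%, 10% and 20%.

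**5. Early stoppers.** They have no Day 5 data to lose, so only Day 1 summaries change. If the lost subject is the highest exposer, the Day 1 geometric mean is multiplied by 0.93, 0.89 and 0.85 at the three CVs. If the lowest, it rises as in step 3.

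**The case against.** The strongest reply is that the SAP has overtaken the list. SAP 2.4 declares the PK set changed, the protocol defers PK detail to a PK SAP, and Protocol 13.3 allows deviations to be recorded in a revised SAP. Under SAP 3.2 alone, early stoppers with a Day 1 profile and subjects with one or two quantifiable values stay. This stands against a reader who infers that low exposers and early stoppers are removed and that exposure is therefore biased: the documents do not settle that. It does not close the point, because SAP 2.4 replaces the set definition and is silent on the list.

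Two further inferences fail. A reader might treat the missing-sample rule as another choice made after seeing results; it is not starred, so it must be decided before bioanalysis. A reader might also expect the effect mainly at the lowest doses. That is plausible, but it depends on an LLOQ that the documents do not give.

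It is also fair that PK is secondary and descriptive, that concentrations are listed by subject and individual profiles plotted, and that omissions would therefore be visible. This limits the harm.

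Finally, simply keeping everyone does not work. Protocol 13.1.5.1 sets below-limit values to zero and withholds a geometric mean when zeros are present. SAP 5.4.4 uses LLOQ/2 in summaries (zero at pre-dose) but sets embedded and terminal below-limit values to missing for parameters. This objection stands, and the remedy must deal with it.

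**Conclusion.** The concern holds in a conditional form. The protocol list permits exclusion on measured exposure after bioanalysis, with one criterion undefined, and its per-subject sample count discards valid Day 1 profiles. The protocol's own inclusion sentence and SAP 3.2 point the other way, so two analysts could build different PK sets from the same data.

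If the list is applied and a low exposer meets it, geometric mean exposure is biased upward and variability understated. The illustration is about 8% to 17% for one of six at assumed CVs of 30% to 70%. It rests on log-normal exposure, on the assumed CVs and on someone meeting the rule; a single very low subject could shift the mean more. The early-stopper rule loses Day 1 data with a bias of unknown direction and leaves Day 5 parameters untouched.

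No powered figure is affected: "No technical sample size calculation was done". The plan should be corrected, but the primary safety objective does not depend on it.

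**What to change.** In the SAP:

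- State that the PK set in 3.2 replaces the list in Protocol 13.1.5.1.
- Delete the very-low criterion.
- Limit the fewer-than-three-quantifiable criterion to parameters that need the terminal slope.
- Apply the missing-sample criterion per profile and per parameter.
- Adopt one below-limit rule in place of the conflicting rules in Protocol 13.1.5.1 and SAP 5.4.4. Under it, keep subjects with no measurable concentration in the concentration summaries, stating this expressly because SAP 3.2 would probably drop them. Report their number beside the geometric mean of each parameter.
- List every exclusion with its reason and its timing relative to bioanalysis.
- Show the PK summaries with and without any subject excluded after bioanalysis.

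A statistical analysis was already done after Cohort 4 (Protocol 13.4, SAP 5.4.6), so the change should be documented as made after that analysis.

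The cost is wording, one more set of PK summaries, and variability that may look larger at low doses.

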13.1.6 Demographic and Other Baseline Characteristics

Subject disposition, demographic and other baseline data will be presented using summary statistics. The Safety set will be used for this presentation.

13.1.7 Exposure to Treatment

The number of IMP administrations will be summarized. Compliance will be calculated as the percentage of actual doses the subject took with respect to the total doses planned. The Safety set will be used for this presentation.

13.1.8 Concomitant Treatment

Concomitant medication and concomitant therapy will be summarized as number of subjects being treated with each type of medication/therapy classified according to ATC level 3 and World Health Organization (WHO) Drug Dictionary preferred term. The Safety set will be used for this presentation.

13.2 Determination of Sample Size

The study will consist of five sequentially recruited cohorts of 8 subjects each, resulting in up to 40 randomized subjects.

No technical sample size calculation was done.

This sample size of 8 subjects per cohort with a randomization 3:1 for active/placebo treatment, is regarded sufficient to demonstrate the effects of the study drug under investigation and therefore to be sufficient to fulfill the objectives of the study.

In case of a withdrawn subject from the study during the treatment period and for other reasons than safety, he/she may be replaced with another subject, at the Sponsor's discretion. All subjects receiving at least one dose of the study medication will be evaluated for safety.

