13.1.2 Statistical Issues

13.1.2.1 Level of Significance, Multiple Comparisons and Multiplicity

Results of statistical analysis will be interpreted descriptively by treatment arm. All statistical models applied will foremost be used as tools for exploring treatment differences between treatment arms rather than formal testing of hypotheses. For this reason, corrections for multiple testing will not be applied in this study and, therefore, confidence intervals (CIs) or p-values indicating statistically significant differences between treatments should be interpreted as suggestive rather than evidence of differences.

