4. STUDY ENDPOINTS AND DERIVED VARIABLES DEFINITION

4.1 General considerations

The following time unit conversion factors will be applied to convert days into weeks, months, or years as needed.

Table 1 Time unit conversion factors

| | |
|---------|--------------|
| 1 week | 7 days |
| 1 month | 30.4375 days |
| 1 year | 365.25 days |

Table 2 Units conversion factors

| | |
|----------|-------------|
| 1 pounds | 0.453597 kg |
| 1 inch | 2.54 cms |

Periods:

Study day: The date of first dose of ATL001 administration is considered as Day 1 of the study.

For the events occurring on or after this day, the study day is calculated as the event date minus the date of the first administration of ATL001 plus 1 day.

For the events occurring before the start of treatment, study day is calculated as the event date minus the date of the first administration of ATL001.

The End of the study is defined as the date of the last study visit of a study subject (“last subject last visit”). The study will be completed after the last subject has performed the safety follow-up 30 days after the last IMP administration (FU-V2).

Baseline value: is defined as the last non-missing observation for each subject prior to the first administration of ATL001.

Difference from Baseline:

Change = Post baseline visit value – baseline value

If either the baseline or visit value is missing, the change from baseline is set to “missing”.

Placebo:

All placebo receiving subjects will be combined into a single placebo group and presented as “Placebo” group.

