5.2 Statistical Hypotheses

No formal statistical hypothesis of the safety or tolerability will be tested for this study.

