5.4 Summary of Statistical Methods

All subjects entered in the database will be included in subject data listings.

All relevant subject data will be included in listings.

The listings will be sorted by placebo/ dose-level cohort, subject, visit, and timepoint where applicable, unless specified otherwise.

All applicable data will be summarized overall. In addition, data will be summarized by visit and/or timepoint when appropriate. Unscheduled or repeat assessments will not be included in summary tables but will be included in listings, if any.

Continuous variables will be summarized using the number of observations (n), missing, mean, standard deviation (SD), median, Q1, Q3, minimum, and maximum along with the total number of subjects contributing values.

Descriptive statistics for categorical/qualitative data will include frequency counts and percentages. The total number of subjects in the cohort (N) will be used as the denominator for percent calculations unless stated otherwise in the table footnote.

Results of statistical analysis will be interpreted descriptively by placebo/ dose-level cohort.

No adjustment for covariates is planned for this study.

No missing value imputation will be done (except for what is included in the missing data imputation section [5.4.8](#))

All analyses will be conducted on observed data.

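### Eight subjects per cohort is called sufficient to show drug effects, but the size does not support this for adverse event incidence, and no confidence interval is specified

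*Protocol*

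**What the plan says.** Protocol 13.2 plans "five sequentially recruited cohorts of 8 subjects each, resulting in up to 40 randomized subjects", with 6 active and 2 placebo in each. It states "No technical sample size calculation was done". It then says that this size "is regarded sufficient to demonstrate the effects of the study drug under investigation" and concludes that the objectives can be met. SAP 5.1 repeats both statements.

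Elsewhere the plan is descriptive. SAP 5.2 states "No formal statistical hypothesis of the safety or tolerability will be tested for this study", and Protocol 13.1 says the same. Protocol 13.1.2.1 adds that "confidence intervals (CIs) or p-values indicating statistically significant differences between treatments should be interpreted as suggestive", not as evidence of differences.

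On presentation, SAP 5.4 says "Descriptive statistics for categorical/qualitative data will include frequency counts and percentages". The adverse event tables in SAP 5.4.3.2 give numbers and proportions of subjects. The PK summaries in SAP 5.4.4 give SE and CV% but no interval. The comparator is defined in SAP 4.1: "All placebo receiving subjects will be combined into a single placebo group".

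**The concern.** The sufficiency sentence is the only rationale for the sample size in either document, and nothing supports it: there is no target rate, effect size, alpha, power or precision. It also conflicts with the rest of the plan. A study that tests no hypothesis, and treats any apparent difference as only suggestive, has not been sized to demonstrate effects.

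The main part of the primary endpoint is an incidence (Protocol 7), and the results are meant to help choose well tolerated doses for later studies (Protocol 6.3, SAP 2.1). With six active subjects per dose, many cells will be 0/6 or 1/6. Shown as a bare percentage, such a cell does not tell the reader how high a true rate it is compatible with. The sufficiency sentence points the reader towards more certainty than the data can give.

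**Working it through.** **Plan's own figure.** 5 cohorts × 8 = 40, of which 5 × 6 = 30 are active and 5 × 2 = 10 are placebo. This agrees with the documents. There is no other sample size figure to reproduce.

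**Inputs.** From the documents: n = 6 per dose (Protocol 10.2) and pooled placebo of about 10 (SAP 4.1; replacements could change this slightly). Assumed, because the documents give none: two-sided alpha of 0.05, and the true event rates shown below.

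**1. Precision of a dose group.** With 0 events in n, the exact (Clopper-Pearson) two-sided 95% upper limit is 1 − 0.025^(1/n).

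| Observed | Exact 95% interval |
|---|---|
| 0/6 | 0% to 45.9% (1 − 0.025^(1/6) = 0.459) |
| 1/6 | 0.4% to 64.1% |
| 2/6 | 4.3% to 77.7% |
| 0/10 (pooled placebo) | 0% to 30.8% |

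The one-sided 95% upper limit for 0/6 is 1 − 0.05^(1/6) = 39.3%.

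**2. Chance of missing an event altogether.** P(0 of 6) = (1 − p)^6. At an assumed p = 10% this is 0.9^6 = 0.531, so the event is seen at least once only 47% of the time. The chance of seeing at least one is 26% at p = 5%, 74% at 20% and 88% at 30%. An 80% chance needs p = 1 − 0.2^(1/6) = 23.5%.

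**3. Comparison with pooled placebo (6 v 10).** Two-sided Fisher exact test, tables with more events on active:

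- Placebo 0/10: at least 3/6 is needed (3/6 gives p = 0.036; 2/6 gives p = 0.125).
- Placebo 1/10: at least 4/6 (4/6 gives p = 0.036; 3/6 gives p = 0.118).
- Placebo 2/10: at least 5/6 (p = 0.035).
- Placebo 3/10 or 4/10: 6/6 only.

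Power is the sum over placebo counts b of P(b) × P(active count reaches the threshold for b). At an assumed placebo rate of 10%, P(b = 0, 1, 2, 3, 4) = 0.349, 0.387, 0.194, 0.057, 0.011.

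- Active 30%: 0.349 × 0.256 + 0.387 × 0.070 + 0.194 × 0.011 + (0.057 + 0.011) × 0.0007 = 0.119, or about 12%.
- Active 50%: 0.349 × 0.656 + 0.387 × 0.344 + 0.194 × 0.109 + (0.057 + 0.011) × 0.016 = 0.384, or about 38%.
- The same calculation gives 70% for 70% v 10% and 84% for 80% v 10%.

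Only a very large difference in incidence would be detected with conventional power.

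**4. Search for intervals.** The protocol mentions confidence intervals in an interpretation caveat (synopsis and 13.1.2.1), without an endpoint, level or method. In the SAP the term appears only in the abbreviation list.

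**The case against.** The strongest reply is that the sentence is loose wording which the plan neutralises itself. The line before it says no calculation was done, no hypothesis is tested, and interpretation is descriptive. No display or decision depends on it, and cohorts of this kind are accepted in phase I. Exact limits can be worked out from the planned n and N. Cohorts 1 to 4 had already been analysed before Cohort 5 enrolled (Protocol 13.4, SAP 5.4.6), so rewording changes no conduct.

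Much of this stands. It limits the point to a justification and a presentation, and rules out several stronger readings that a reader might infer:

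- *The cohorts are too small.* The documents set no precision or power target that the design fails, and the aim is descriptive.
- *Each cohort's 6 active subjects are compared with its own 2 placebos.* SAP 4.1 pools placebo, so no such comparison is planned.
- *The SAP dropped an interval that the protocol promised.* Protocol 13.1.2.1 is a caveat about interpretation and commits to no interval.
- *Escalation will rest on a 0/6 cell.* It rests on DSMB review, the stopping rules and the dose-limiting toxicity criteria (Protocol 8.1.1 to 8.1.3).

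The table shells listed in SAP 7 are separate documents and may contain intervals; the SAP text does not call for them.

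What does not stand is that the disclaimers make the sentence harmless. It asserts that the objectives are met, it appears in both documents, and it contradicts those disclaimers. Exact intervals are descriptive and test nothing, so a descriptive plan is no reason to omit them.

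**Conclusion.** The point holds as one of wording and reporting. Nothing in either document supports the claim that 8 per cohort suffices to demonstrate drug effects, and for adverse event incidence the design does not have that property. No confidence interval is specified for any endpoint.

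The interval limits in step 1 depend only on the planned group sizes. The 53% figure rests on an assumed 10% event rate, and the 12% and 38% on assumed rates and an assumed alpha; they describe what the size could show, not a planned test. PK precision was not assessed, because the documents give no variability figure.

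A reader might also take comfort from the pooled figure: 0/30 on active has an upper limit of 1 − 0.025^(1/30) = 11.6%. That averages over a 20-fold dose range (0.2 to 4 mg/kg) and does not bound the rate at the highest dose.

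**What to change.** **Protocol 13.2 and SAP 5.1.** Replace the sufficiency sentence with something like: *The sample size is based on feasibility and usual phase I practice. The study is not sized to demonstrate differences from placebo. With 6 active subjects at a dose, 0 events is compatible with a true incidence of up to 46% (exact 95% interval).* The sponsor should confirm that the first sentence is the true basis.

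**SAP 5.4.3.2.** Add exact (Clopper-Pearson) 95% intervals to the subject-level incidence of any TEAE, grade ≥2 TEAE and gastrointestinal TEAE, for each dose and for pooled placebo. Grade ≥2 is the level used in the protocol's dose-limiting toxicity criteria (8.1.3), but the SAP overview table breaks out only grade 3 and above. Gastrointestinal toxicity is the one identified risk in Protocol 6.5, but the overview has only AESI rows, and Protocol 12.5 restricts AESIs to treatment-related gastrointestinal events. If an interval for all ATL-001 subjects is shown, add a footnote that it averages over 0.2 to 4 mg/kg and does not bound the rate at the highest dose.

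**Cost.** A few added table rows, one column of intervals and a less favourable stated claim.
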